- **NOTE:** Eligible patients will be allowed to have multiple risk factors, and there will not be a limit as to how many of the above risk factors a subject may have. In addition, we will place no limit on the number of patients included with multiple risk factors. A study population with multiple risk factors is highly representative of the provoked VTE population and will provide the greatest generalizability of the study results to real-world clinical practice. Including patients with single and multiple persistent provoking risk factors will also facilitate enrollment. As noted, there is clinical and research equipoise regarding whether patients with a single or multiple persistent provoking VTE risk factors should receive extended duration thromboprophylaxis for secondary prevention.
- Willing to provide written informed consent

Study Exclusion Criteria

- Women who are pregnant or breastfeeding
- Women of child-bearing potential who are unwilling or unable to use an acceptable method of birth control (such as oral contraceptives, other hormonal contraceptives [vaginal products, skin patches, or implanted or injectable products], or mechanical products such as an intrauterine device or barrier methods [diaphragm, condoms, spermicides]) to avoid pregnancy for the entire study
- Active cancer within the past 5 years
- Contraindication to antithrombotic or antiplatelet therapy
- Requirement for ongoing anticoagulant therapy, dual antiplatelet therapy, P2Y12 inhibition, or aspirin at a dose of > 81 mg daily
- Hemoglobin level < 9 mg/dL, a platelet count < 100,000/mm³, a serum creatinine level > 2.5 mg/dL or CrCl < 25 mL/minute (as determined by Cockcroft-Gault equation), an ALT or AST level > 2 times the upper limit of the normal range, or a total bilirubin level > 1.5 times the upper limit of the normal range
- History of a platelet disorder such as Von Willebrand Disease
- History of bleeding diathesis or have had recent active bleeding
- Active severe hepatobiliary disease
- More than 6 months that have elapsed without taking an anticoagulant or low-dose aspirin
 - **NOTE:** The risk of recurrent VTE following cessation of anticoagulation rises slowly over the first 3-6 months (26). After this initial period, the cumulative risk of recurrent VTE steepens. Using a limit of no greater than 6 months of interruption in anticoagulation before potential re-initiation of anticoagulation as part of this trial will safely facilitate

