 - b. Review of relevant laboratory data from within the past three months. If laboratory data for a complete blood count, basic chemistry panel, and coagulation (prothrombin time and activated partial thromboplastin time) are not available from the past three months, these will be drawn at the initial study visit and paid for by the study.
 - c. Serum (β -HCG) or urine pregnancy test (u-HCG) for women of child-bearing potential
7. If the potential study subject does not meet all the inclusion criteria or meets any of the exclusion criteria, the rationale for exclusion from the study will be recorded in the screening section of the electronic case report form (eCRF).

Assessment of Enrollment

After 10 months of study recruitment, an assessment of enrollment will be conducted. If 300 study subjects have not been recruited by 10 months, activation of second study site, Brigham and Women's Faulkner Hospital, will be considered by the Study Investigators. Activation of the Brigham and Women's Faulkner Hospital as a study site will require submission to and approval by the Partners Human Research Committee/IRB.

Treatment Description

Subjects will begin anticoagulation within 3 weeks of passing the screening procedure. Subjects who are 18 years of age or older with provoked DVT and/or PE, have completed at least 3 months of therapeutic anticoagulation, have a low risk of bleeding, and have at least one persistent provoking risk factor will be randomly assigned to receive apixaban 2.5 mg orally twice daily or oral placebo for extended secondary prevention of VTE for a duration of 12 months.

If during the study period the patient requires an invasive procedure or surgery that necessitates the discontinuation of anticoagulation (study drug), apixaban should be held as per the prescribing guidelines (**Appendix**, http://packageinserts.bms.com/pi/pi_eliquis.pdf). If appropriate based on the judgment of the responsible clinician, apixaban should be restarted when safe to do so postoperatively.

Patients and providers will be blinded as to the study group assignment.

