- Musculoskeletal and connective tissue disorders: muscle hemorrhage
- Reproductive system and breast disorders: vaginal hemorrhage, metrorrhagia, menometrorrhagia, genital hemorrhage
- Vascular disorders: hemorrhage
- Skin and subcutaneous tissue disorders: ecchymosis, skin hemorrhage, petechiae
- Eye disorders: conjunctival hemorrhage, retinal hemorrhage, eye hemorrhage
- Investigations: blood urine present, occult blood positive, occult blood, red blood cells urine positive
- General disorders and administration-site conditions: injection-site hematoma, vessel puncture-site hematoma

Additional information about the risks of apixaban can be found in the Apixaban Med Guide (see Appendix).

Protection of Subjects against the Risks of Research Procedures

Before Study Enrollment

A rigorous screening process will be utilized to ensure that subjects with an increased risk of harm due to enrollment in the study are excluded from the study. This will include performing a detailed history and physical examination (to ensure that enrolled subjects truly fulfill all eligibility criteria) and carefully reviewing the results of laboratory testing (in particular, hematocrit, platelet count, INR, and serum creatinine).

During Follow-Up

Changes in health status during the 12-month follow-up period will be evaluated by the patient's primary physician, and other routine providers. All subjects enrolled will also have ongoing medical care with a dedicated Vascular Medicine provider. As apixaban is an FDA-approved drug commonly used for thromboprophylaxis and does not require routine follow-up clinical or laboratory monitoring for toxicity, the study will not mandate any follow-up visits or procedures other than those required for the patient's routine care.

Protection against Loss of Confidentiality

Subject confidentiality will be protected by maintaining all paper records in locked file cabinets in locked offices and all electronic records in password-protected computer files. All study data will be de-identified for storage in the electronic data repository. In addition, any identifying information will be removed from images or other data used in publication or presentations. All database information will be stored on computer systems that are located behind an electronic firewall, which will only permit access to certified study personnel. Access to study data files will be password-protected.

Use of Information and Publication

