	
S, or antithrombin), dual antiplatelet therapy, P2Y12 inhibition, or aspirin at a dose of >81 mg daily
 
[] Hemoglobin level < 9 mg/dL, a platelet count < 100,000/mm³, a serum creatinine level > 2.5 mg/dL, an ALT or AST level > 2 times the upper limit of the normal range, or a total bilirubin level > 1.5 times the upper limit of the normal range
 
[] History of a platelet disorder such as Von Willebrand Disease
 
[] History of bleeding diathesis or have had recent active bleeding
 
[] Active hepatobiliary disease
 
[] More than 6 months that have elapsed without taking an anticoagulant or low-dose aspirin
 
[] Known severe thrombophilia (any increased titer antiphospholipid antibody or positive lupus anticoagulant/DRVVT or deficiency of antithrombin, protein C, or protein S)
 
[] Life expectancy < 12 months or hospice care
 
[] Prisoners or subjects who are involuntarily incarcerated
 
[] Subjects who are compulsorily detained for treatment of either a psychiatric or physical (e.g., infectious disease) illness
 
[] Receiving concurrent non-FDA-approved or investigational agents or has received an investigational agent within the past 30 days prior to the first dose of study treatment (with the exception of approved medications being used for an approved indication, e.g., investigating a new dosing regimen for an approved indication).
 
[] Any condition, which in the opinion of the investigator, would put the subject at an unacceptable risk from participating in the study
 
[] Any other medical, social, logistical, or psychological reason, which in the opinion of the investigator, would preclude compliance with, or successful completion of, the study protocol

STOP HERE AND DO NOT ENROLL PATIENT IF ANY OF THE INCLUSION CRITERIA ARE ABSENT OR ANY EXCLUSION CRITERIA ARE PRESENT
	
Eligible	[] Yes [] No
Written informed consent signed	[] Yes [] No

Patient Demographics	
Study ID number	-----
Date of enrollment	____ / ____ / ____ MM DD YYYY
Date of birth	____ / ____ / ____ MM DD YYYY
Gender	 Male  Female
Ethnicity	 Hispanic/Latino  Non-Hispanic/Non-Latino

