4.2 Safety Outcomes

4.2.1 Principal Safety Outcome

The principal safety outcome will be the time to first major bleeding within 12 months from randomization. Major bleeding is defined according to the International Society on Thrombosis and Haemostasis (ISTH) as overt bleeding that is associated with a decrease in the hemoglobin level ≥ 2 g/dL, leads to transfusion ≥ 2 units of packed red blood cells, occurs in a critical site, or contributes to death 1. The principal safety outcome will be independently adjudicated by a blinded CEC review. Non-hemorrhagic death will be considered a competing risk for this outcome.

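### Three laboratory eligibility criteria are not carried through consistently: creatinine clearance is missing from the enrolment form and SAP, no liver-test draw is specified, and the haemoglobin limit is printed in mg/dL

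*Combined protocol and SAP*

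**What the plan says.** References are to the final protocol (11/19/2021) and the SAP.

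**Renal.** Study Exclusion Criteria exclude serum creatinine above 2.5 mg/dL or "CrCl < 25 mL/minute (as determined by Cockcroft-Gault equation". The CRF exclusion checklist, which ends in an instruction not to enrol if any item is present, has "a serum creatinine level > 2.5 mg/dL, an ALT or AST level > 2 times the upper limit of the normal range", with no clearance term between the two. A later CRF item asks only whether creatinine exceeds 2.5 mg/dL, yes or no. The list under Study Population that defines low bleeding risk, and SAP 3.3, also give creatinine alone.

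**Liver.** The exclusion list bars "an ALT or AST level > 2 times the upper limit of the normal range" and a raised total bilirubin. Item 6b of Screening Procedures calls for "Review of relevant laboratory data from within the past three months". It then continues "If laboratory data for a complete blood count, basic chemistry panel, and coagulation (prothrombin time and activated partial thromboplastin time) are not available" from that period, in which case those tests are drawn at the initial visit. The section on protecting subjects before enrolment stresses laboratory review, "in particular, hematocrit, platelet count, INR, and serum creatinine".

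**Haemoglobin.** The exclusion is "Hemoglobin level < 9 mg/dL", and the same unit appears in the low-bleeding-risk list, the CRF checklist and SAP 3.3. The major-bleeding definition in the protocol and in SAP 4.2.1 uses "a decrease in the hemoglobin level ≥ 2 g/dL".

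**The concern.** These criteria are checked before a patient is randomised to an anticoagulant or placebo, in a trial whose primary safety outcome is major bleeding and whose population is described as being at low bleeding risk. The form staff use to decide enrolment should therefore apply the same criteria as the protocol, and the planned tests should be enough to check them.

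A coordinator following the CRF can enrol a patient whom the protocol excludes on clearance. Chronic kidney disease (eGFR below 60) is a qualifying risk factor and there is no upper age limit, so reduced renal function will be seen at screening. The protocol also uses clearance after enrolment: a confirmed fall below 30 mL/min is a withdrawal criterion.

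For the liver criteria, a patient without recent results has no specified route to being measured. Table 8 (Study Calendar) has no laboratory row, and Follow-Up Evaluation requires no routine testing later. A threshold in the wrong unit on an enrolment form is a plain error in a stated eligibility rule.

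**Working it through.** The plan gives no figure to reproduce on this point, so the check is a comparison of the texts, a unit conversion and a test of whether the clearance criterion is redundant.

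**1. The texts side by side**

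| Place | Renal | Liver | Haemoglobin unit |
|---|---|---|---|
| Study Population, low-bleeding-risk list | creatinine only | ALT/AST, bilirubin | mg/dL |
| Study Exclusion Criteria | creatinine or CrCl < 25 mL/min | ALT/AST, bilirubin | mg/dL |
| CRF exclusion checklist | creatinine only | ALT/AST, bilirubin | mg/dL |
| CRF creatinine item | creatinine only, yes/no | – | – |
| SAP 3.3 | creatinine only | ALT/AST, bilirubin | mg/dL |
| Screening item 6b, drawn if missing | basic chemistry panel (contents not listed) | none named | (blood count) |
| Major-bleeding definition, protocol and SAP 4.2.1 | – | – | g/dL |

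**2. Is the clearance criterion redundant with creatinine above 2.5 mg/dL?** The documents name Cockcroft-Gault but do not print it. I take the usual form as an assumption: CrCl = (140 − age) × weight / (72 × creatinine), times 0.85 for a woman. Ages and weights below are also assumptions.

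- Woman, 80 years, 50 kg, creatinine 1.5: 60 × 50 / (72 × 1.5) × 0.85 = 23.6 mL/min.
- Woman, 85 years, 45 kg, creatinine 1.6: 55 × 45 / (72 × 1.6) × 0.85 = 18.3 mL/min.
- Man, 80 years, 70 kg, creatinine 2.4: 60 × 70 / (72 × 2.4) = 24.3 mL/min.

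All three meet the protocol exclusion and pass the CRF.

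Setting CrCl = 25 gives the creatinine above which a patient falls under the clearance exclusion: (140 − age) × weight × (0.85 if female) / 1800. Where this is below 2.5 mg/dL, the CRF misses patients between that value and 2.5.

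| Assumed profile | Creatinine at CrCl 25 (mg/dL) | Missed range |
|---|---|---|
| 85 y, 50 kg, woman | 1.30 | 1.30 to 2.5 |
| 75 y, 50 kg, woman | 1.53 | 1.53 to 2.5 |
| 85 y, 70 kg, woman | 1.82 | 1.82 to 2.5 |
| 85 y, 70 kg, man | 2.14 | 2.14 to 2.5 |
| 75 y, 70 kg, woman | 2.15 | 2.15 to 2.5 |
| 75 y, 70 kg, man | 2.53 | none |
| 65 y, 90 kg, woman | 3.19 | none |
| 65 y, 90 kg, man | 3.75 | none |

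Over a grid of ages 50, 65, 75 and 85, weights 50, 70, 90 and 110 kg and both sexes, 12 of 32 profiles have a missed range: 7 of 8 at 50 kg, 4 of 8 at 70 kg, 1 of 8 at 90 kg and none at 110 kg. The grid shows where the gap lies; it is not a population and gives no frequency.

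**3. Could clearance be checked from the CRF?** The formula needs age, sex, weight and creatinine. The CRF pages shown record date of birth and sex, but body size only as BMI and creatinine only as above 2.5 or not.

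**4. Haemoglobin.** 9 mg/dL = 9/1000 = 0.009 g/dL. That is 0.009/2 = 0.45% of the 2 g/dL fall that counts towards major bleeding, so as printed the criterion excludes nobody.

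**The case against.** Much can be said for the plan. Screening item 3 requires the investigator to confirm that every exclusion is absent, and item 6b asks for review of relevant laboratory data, not just the listed tests. The liver exclusion is itself on the CRF checklist. The contents of the basic chemistry panel are not defined, and the list of stressed tests is not presented as exhaustive. SAP 3.3 is a prose summary that admits nobody. A CRF need not hold every eligibility input, because source documents and the health record stand behind it. No clinician would apply 0.009 g/dL. The clearance examples are light or close to the limit, and obesity is a qualifying factor, so many recruits will be heavy.

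Most of this limits the point without removing it. The duty to confirm all exclusions stands, so one cannot say that liver function goes unchecked; but the plan does not specify the draw needed to meet that duty when results are missing. The haemoglobin unit is very likely a slip that readers will see through, yet it is on the enrolment form. The weight argument is right about frequency, but the CRF still contradicts the protocol for the patients in the gap.

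A reader might also infer three stronger things that the documents do not support:

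- That clearance is part of the low-bleeding-risk definition. It is not: that list has creatinine only.
- That the renal exclusion is absent from the CRF. The creatinine half is there twice; only the clearance alternative is missing.
- That the withdrawal trigger of ALT or AST at 3 times the upper limit of normal has nothing to be judged against. It is a multiple of the normal limit and needs no baseline; a baseline would at most help in judging whether the study drug is the suspected cause.

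**Conclusion.** The point holds as three inconsistencies in carrying eligibility criteria through the documents.

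The renal mismatch matters most. An enrolment form followed as written can admit older, lighter patients whom the protocol excludes. This rests on the usual Cockcroft-Gault formula and on assumed profiles. For heavier or younger patients the creatinine limit is usually reached first, and the number affected cannot be derived. The liver gap is that no draw is specified when results are missing; how many patients lack them is not stated. The haemoglobin unit is probably a typographical error repeated in four places. The platelet and creatinine limits work as written.

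The criteria apply before randomisation and to both arms alike, so no bias in the treatment comparison is shown, and the sample size is unaffected. What is at stake is whether enrolled patients meet the stated criteria. The absence of weight and creatinine fields is judged on the CRF pages available; the text breaks off within the outcomes section, after the screening and baseline pages.

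**What to change.** 1. **Renal criterion.** The sponsor should reconcile the criterion across Study Population, Study Exclusion Criteria, the CRF checklist, the CRF creatinine item and SAP 3.3, so that the form deciding enrolment matches the protocol. No threshold is proposed here. Record weight and the creatinine value on the CRF. The creatinine field would also serve SAP 6.3, which plans a mean and SD for serum creatinine. Cost: wording and two fields.
2. **Liver tests.** Name ALT, AST and total bilirubin in item 6b, on the draw already planned for patients without recent results, with results available before randomisation. Cost: slightly higher laboratory expense, for those patients only.
3. **Haemoglobin.** Correct the unit in all four places (Study Population, Study Exclusion Criteria, CRF checklist, SAP 3.3), consistent with the g/dL of the bleeding definition. Cost: wording only.

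For patients already enrolled, the same items can be checked retrospectively in the electronic health record, which the protocol already uses for data abstraction, where the values were recorded.
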